#### **4.1.3 Post-Treatment Follow-Up Period**

After completing the Treatment Period, subjects proceed to the post-treatment Follow-up Period and will return for the End of Study (EOS) visit. The choice of anemia treatment during the Follow-up Period is up to the discretion of the Investigator. If the Investigator decides to resume ESA treatment in roxadustat treated subjects, the first dose of ESA should be administered at least three days after the last dose of roxadustat.

#### **4.1.4 Long-term Follow-Up for Premature Treatment Discontinued Subjects**

Subjects who discontinue study medication prematurely will be followed up for vital status, CV events, and hospitalization until study closure, unless consent to participate is withdrawn. Upon completion of EOT and EOS visits, these subjects will be followed up every 3 to 6 month interval (depending on the availability of subjects) until study closure. These visits may occur either in-person or via telephone.

### **4.2 Randomization, Treatment Assignment, and Rationale for Open-label Design**

A randomized design has been chosen in order to ensure a balanced and unbiased allocation of study subjects to the treatment arms and to minimize bias in therapeutic management and in outcomes assessment.

An open-label design was chosen since double-blinding would require a double-blind, double-dummy design to match the different ESAs made by different manufacturers having different dosing specifications which is considered too challenging without much added benefits to the study. It would expose subjects to multiple additional injections or infusions without additional benefit. Furthermore, the difference in iron supplementation requirements between roxadustat and the ESA will further complicate any efforts to blind, or alternatively end up in inadvertent unblinding. The high probability of these confounding factors rendering the conduct of a double-blind double-dummy study and data becoming invalid is outweighing the advantage of a lower risk for bias. Therefore, in light of the objectivity of primary endpoint measures not influenced by blinding and the lack of operational feasibility without addition of values to subjects, the open label study design is to be considered the most reasonable option.

A total of up to approximately 1200 subjects are planned to be randomized in an open-label, 1:1 ratio to receive either of the following two treatments:

- Roxadustat (up to approximately 600 subjects)
- Active Control: epoetin alfa (up to approximately 600 subjects)

Randomization is stratified by the following four factors:

- Mean qualifying screening Hb ( $\leq 10.5$  vs.  $> 10.5$  g/dL)
- History of CV, cerebrovascular, or thromboembolic diseases (Yes vs. No)
- Mean prescribed weekly baseline epoetin alfa dose (or, equivalent epoetin dose for non-epoetin subjects) in the 4 weeks prior to randomization ( $\leq 150$  vs.  $> 150$  IU/kg/week)

- Geographical region (US vs. Ex-US region)

Randomization of qualified subjects will take place prior to administration of study drug.

### **4.3 Procedures for Handling Incorrectly Enrolled or Randomized subjects**

Subjects who fail to meet the eligibility criteria should not, under any circumstances, be enrolled or receive study medication. There can be no exceptions to this rule. Where a subject does not meet all the eligibility criteria but is randomized in error or incorrectly received study medication, the Investigator should inform the Medical Monitor immediately, and a discussion should occur regarding whether to continue or discontinue the patient from treatment. All decisions from such meeting should be appropriately documented.

### **4.4 Replacement of Subjects**

Subjects who drop out prematurely will not be replaced in the study.

### **4.5 Study Treatment**

#### **4.5.1 Dose and Schedule**

Eligible subjects will be randomized via IWRS to receive either roxadustat or epoetin alfa. The first dose of study drug should be administered on Day 1 (Week 0), which should correspond to a day when their next dose of ESA would have been administered. All subjects will attend weekly study visits from Day 1 to Week 2, followed by every two weeks study visits from Weeks 4 to 24. Following Week 24, study visits will occur every four weeks until the EOT. Subjects will receive study medication in an open label manner.

#### **4.5.2 Starting Dose of Study Drug**

##### **4.5.2.1 Roxadustat Arm**

In subjects on HD or PD or HHD randomized to roxadustat, the initial roxadustat dose will be determined using a conversion table based on the subject's previous average weekly prescribed ESA dose in the last 4 weeks prior to randomization if the subject is on epoetin or darbepoetin, and average monthly (4 weeks) prescribed ESA dose in 8 weeks prior to randomization if the subject is on Mircera® (Table 2). If the mean qualifying screening Hb value at randomization is < 10 g/dL, the starting roxadustat dose will be increased by one dose step. For example, a subject on epoetin (ie, epoetin alfa, beta, theta, zeta, delta, or omega) 6,000 IU/week with mean screening Hb of 9.4 g/dL at randomization will start roxadustat at a dose of 150 mg three times weekly (TIW).

If the converted initial dose exceeds the maximum dose of 3.0 mg/kg/dose then the lower dose step should be chosen as the initial dose.

The dose of roxadustat will remain constant during the first 4 weeks of the Treatment Period unless a dose reduction is required for excessive hematopoiesis.

**Table 2. Initial Dosing of Roxadustat: Conversion Table from ESAs to Roxadustat**

Epoetin (ie, alfa, beta, theta, zeta, delta, or omega) a (IU/wk)	Darbepoetin alfa a, b (µg/wk)	Mircera ® c (µg/monthly)	Roxadustat Dose d (mg/dose) TIW
< 5,000	< 25	< 80	70
5,000 to 8,000	25-40	80-120	100
> 8,000 to 16,000	> 40-80	> 120-200	150
> 16,000	> 80	> 200	200

Abbreviations: ESA = erythropoiesis-stimulating agent; Hb = hemoglobin; IU = international units; TIW = three times a week; wk(s) = week(s).

- a Average weekly prescribed dose in last 4 weeks prior to randomization
- b If darbepoetin is used biweekly, use half the dose to get per week dose
- c Average prescribed monthly (4 wks) dose in last 8 weeks prior to randomization
- d Starting dose will be one step higher if the mean Hb at randomization is < 10.0 g/dL, however, not to exceed 3.0 mg/kg/dose.

Notes: The roxadustat dose steps are 20, 40, 50, 70, 100, 150, 200, 250, 300, and 400 mg.

#### 4.5.2.2 Epoetin Alfa Arm (Active Control)

Subjects randomized to the epoetin alfa arm who are currently taking non-epoetin alfa treatment will be switched to epoetin alfa treatment on Day 1. All subjects on HD will receive IV epoetin alfa TIW starting from Day 1, irrespective of their baseline route of administration or frequency of ESA use. Subjects requiring ultra-low dose of EPO (eg, ≤1000 IU/per week), frequency of administration may be adjusted per local standard of care.

Subjects on PD or HHD may continue using the same route of administration as baseline; however, if the Investigator decides to change the route of administration in a PD or HHD subject from subcutaneous to IV after randomization it should be done during the early part of the treatment phase (preferably prior to Week 16).

All epoetin alfa administrations should be performed by the Investigator or an authorized member of the site staff or other trained personnel. In subjects on PD or HHD, epoetin alfa may be self-administered subcutaneously by the subject or a caregiver after adequate training or, if in the opinion of the Investigator, the subject or a caregiver is already adequately trained in self-administering ESA prior to the study.

#### Doses:

In subjects who have been randomized to the epoetin alfa treatment arm, the initial epoetin alfa dose that the subject will receive on Day 1 will be determined using a conversion table based on the subject's average weekly prescribed ESA dose in 4 weeks prior to randomization if on epoetin or darbepoetin, and average monthly (4-week) prescribed ESA dose in 8 weeks prior to randomization if on Mircera® (Table 3).

In case of a change in route of administration from subcutaneous to IV (TIW), the initial dose of IV epoetin alfa will be determined by the Investigator per local standard of care.

In subjects on PD or HHD, if receiving epoetin alfa subcutaneously, the dose and frequency may be determined by the Investigator per local standard of care.

Subsequent epoetin alfa dosing and dose adjustment during the study, if indicated, should be based on the country specific package insert or SmPC.

For countries using prefilled epoetin alfa syringes, the initial dose and subsequent dosages following dose adjustments during the Treatment Period should be approximated to the closest total weekly dose.

**Table 3. Initial Dosing of Epoetin Alfa: Conversion table from Non-Epoetin ESAs to Epoetin Alfa**

Baseline ESA	Conversion Ratio	Examples of Converted Initial Epoetin Alfa dose (approximate) IU/week c
Epoetin (ie, alfa, beta, theta, zeta, delta, or omega) (IU/week) a	x 1	6,000 IU/week x 1 = 6,000 IU/week
Darbepoetin alfa (µg/week) a	x 200	40 µg/week x 200 = 8,000 IU/week
Mircera ® (µg/once monthly (ie, 4-wks) b	x 70 – 80 (for lower Mircera ® dose lower conversion ratio may be used) d	100 µg/month x 70 = 7,000 IU/week  200 µg/month x 80 = 16,000 IU/week

Abbreviations: ESA = erythropoiesis-stimulating agent; IU = international units.

- a Mean weekly ESA in 4 weeks prior to randomization
- b Mean monthly (4-week) ESA in 8 weeks prior to randomization
- c May be rounded as deemed necessary by the investigator
- d Per discretion of the investigator

### 4.5.3 Dose Adjustment

#### 4.5.3.1 Roxadustat Arm

During the Treatment Period, roxadustat dose adjustment will be made according to the dose adjustment algorithm in Appendix 2, in order to maintain a Hb level of approximately 11 g/dL. Roxadustat dose adjustments are permitted from Week 4 onwards, and every 4 weeks thereafter (eg, Week 4, Week 8, Week 12); however, dose may be adjusted between two prespecified windows (eg, anytime between Week 4 and Week 8 visits, Week 8 and Week 12 visits) if the following two criteria are met:

- No dose adjustment has been made in last 4 weeks,
- Hemoglobin (Hb) < 9.0 g/dL.

Subjects on HD or PD or HHD randomized to roxadustat will take doses TIW for the entire duration of the Treatment Period. If a subject requires < 20 mg TIW (ie, < 60 mg per week) to maintain a Hb level of approximately 11 g/dL, the dosing frequency should be reduced in a step-wise fashion e.g. TIW to BIW, BIW to QW, QW to Q-2 Week etc.

In this study, a rate of rise of Hb > 2 g/dL within 4 weeks or a Hb level of  $\geq$  13 g/dl at any time would be considered as excessive haematopoiesis. For a rate of rise of Hb > 2 g/dL within 4 weeks, dose should be reduced by one dose step and for a Hb value  $\geq$  13.0 g/dL, the dose should be on hold until Hb drops < 12.0 g/dL per guidelines provided in the protocol (Appendix 2). When roxadustat will be resumed, the dose will be reduced by one dose step.

Dose adjustments or temporary dose holds for excessive hematopoiesis can occur at any time during the Treatment Period. Any dose adjustment will reset the dose-adjustment window to every 4 weeks thereafter (eg, dose adjustment for a qualified reason at Week 6 leads to next dose adjustment at Week 10). If a dose adjustment review is scheduled on Week 22, then the next dose adjustment review will be scheduled on Week 28, since there is no scheduled visit on Week 26.

Prescribed dose must not exceed the maximum allowable dose of 3.0 mg/kg/dose or 400 mg per dose, whichever is lower. For dose adjustment purposes, post-dialysis weight (dry-weight) should be used. If the post-dialysis weight of the current visit is not available at the time of dose adjustment, post-dialysis weight of the prior dialysis session or last recorded post-dialysis weight may be used.

#### **4.5.3.2 Active Control (Epoetin alfa) Arm**

Epoetin dose adjustments during the Treatment Period should be based on country-specific epoetin alfa Package Insert or SmPC.

In subjects on PD or HHD, if receiving epoetin alfa subcutaneously, the dose and frequency may be determined by the Investigator per local standard of care.

## **4.6 Concomitant Medications, Procedures and Nondrug Therapies**

### **4.6.1 Concomitant Medications**

Concomitant medications are any prescription or over-the-counter preparations, including herbal products and “natural remedies”, used by a subject while participating in this clinical study.

For all concomitant medication use, an indication for its use should be provided. If the stated indication is a nonspecific condition (eg, “rash”), documentation of the condition, as specific as possible, should be maintained in the subject’s clinical study records as source documentation.

Use of herbal medicine during the study is not prohibited but strongly discouraged. All herbal and natural remedies should be reviewed by the investigator and if considered safe, may be allowed to continue at the same dose.

To avoid confounding effects on study endpoints, changes to anti-hypertensive medications should be minimized, and made only if deemed medically necessary by the Investigator.

#### **4.6.1.1 Phosphate Binders**

When coadministered with roxadustat, in a clinical pharmacology study, the bioavailability of roxadustat was reduced. Subjects should be advised to discuss with the Investigator when

changing the dose or dosing time of their phosphate binder while taking roxadustat. To optimize the absorption of roxadustat, subjects should be advised that roxadustat be taken at least one hour before or three hours after their phosphate binder if possible.

#### 4.6.1.2 Statins

When coadministered with roxadustat, in clinical pharmacological studies, hydroxymethylglutaryl coenzyme A reductase inhibitor (statin) exposure was increased 2- to 3-fold. For patients randomized to roxadustat, investigators should consider this interaction and local prescribing information when deciding on the appropriate statin dose for individual patients, bearing in mind the impact of ethnicity, other concomitant medications, renal and hepatic function. Goals of lipid lowering treatment should be maintained as clinically indicated. The dose of statins should not exceed the recommended daily dose in the table below for subjects randomized to roxadustat.

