##### 3.2.2 Secondary Efficacy Endpoints

The secondary efficacy endpoints in this study are:

- US (FDA) submission: Proportion of subjects with mean Hb level during the evaluation period defined as Week 28 until Week 52  $\geq 10.0$  g/dL.
- EU regulatory submission: Hemoglobin (Hb) response, defined as mean Hb during Weeks 28 to 36 within the target range of 10.0 to 12.0 g/dL without having received rescue therapy within 6 weeks prior to and during this 8-week evaluation period.
- Average monthly IV iron use per subject during Weeks 1 to 36 (monthly defined as a period of 4 weeks).
- Change from BL in low-density lipoprotein (LDL) cholesterol to the average LDL cholesterol of Weeks 12 to 28
- Change from BL in SF-36 Physical Functioning (PF) subscore to the average PF subscore of Weeks 12 to 28
- Change from BL in SF-36 Vitality (VT) subscore to the average VT subscore of Weeks 12 to 28
- Effect on predialysis BP:
  - Time to an exacerbation of hypertension from BL during Weeks 1 to 36

- An increase from BL of  $\geq 20$  mm Hg systolic blood pressure (sBP) and sBP  $> 170$  mmHg

OR

- An increase from BL of  $\geq 15$  mm Hg diastolic blood pressure (dBP) and dBP  $> 100$  mmHg
- Change from BL in mean arterial pressure (MAP) to the MAP value averaged over Weeks 20 to 28

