#### 7.1.1 Screening Period

Subjects must be consented before any screening tests or assessments are performed. All screening procedures should be completed within 6 weeks. For subjects currently taking Mircer®, the screening period can be extended up to 8 weeks. During the screening period eligibility assessments will be performed.

Subjects in screening will continue their existing ESA therapy for the treatment of anemia associated with ESRD.

##### 7.1.1.1 Screening 1

- Signed written informed consent
- Inclusion/Exclusion criteria verification
- Demographics and medical history
- Height and weight (use dry weight in HD subjects)
- Vital signs (BP, HR, respiratory rate [RR], and temperature [Temp])
- Laboratory tests:
  - Complete blood count (CBC) with WBC differential
  - Serum chemistry
  - Serum lipid panel
  - Serum iron, ferritin, total iron-binding capacity (TIBC), unsaturated iron-binding capacity (UIBC), transferrin saturation (TSAT)
  - Reticulocyte count and hemoglobin in reticulocytes (CHr)
  - Hemoglobin A1c (HbA1c)
  - Vitamin B12 and folate
  - Enzyme-linked immunosorbent assay (ELISA) for HIV
  - Hepatitis B surface antigen (HBsAg)

- Anti-HCV Ab
- Review and record concomitant medications
- Review and record procedures and nondrug therapies
- Review and record AEs, if any (capture the event under medical history, if applicable)

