10 PRIOR AND CONCOMITANT MEDICATIONS

The World Health Organization Drug Dictionary (WHODD) will be used to classify prior and concomitant medications by therapeutic class and generic name based on ATC code level 3. Prior medication is defined as any medication taken and stopped prior to the first dose of the study medication within 30 days before signing the informed consent. Concomitant medication is defined as any medication taken between the day of first dose of the study medication and the day of ET/EOT Visit date + 28 days, inclusive.

Medication start and end dates will be compared with the start date of study drug and classified as per Table 4.

In case of partial or missing dates, comparisons will be made based on the level of detail available. For example, if start date of study drug is 04Jan2013, and a medication has a start date of 04Jan2013, the medication will be classified as concomitant. A start date of Jan2013 (i.e., missing day) would also see the medication classified as concomitant.

Table 4. Classification of Prior and Concomitant Medications

Start date \ End date	Before start of study drug administration	On or after start of study drug administration	Missing
Before start of study drug administration	Prior	Concomitant	Concomitant
On or after start of study drug administration	–	Treatment Emergent Concomitant	Treatment Emergent Concomitant
Missing	Prior	Concomitant	Concomitant

Both prior and concomitant medication usage will be summarized by the number and proportion of subjects in each treatment group. Subjects will only be counted one time in each unique ATC Class and generic name if multiple drugs are used by a subject.

Detailed analyses may be performed on prior and concomitant medications of special interests such as oral iron, blood pressure medications and lipids medications.

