11.2 Analysis of Secondary Endpoints

11.2.1 Secondary Endpoints and Hypothesis Testing

Once the null hypothesis of the primary endpoint has been rejected, the secondary endpoints below will be tested using a fixed sequence testing procedure, in order to maintain the overall two-sided type I error of 0.05. If the claim of superiority or non-inferiority is successful and the test will progress to the next comparison in sequence as follows.

Table 6 Key Secondary Endpoints Fixed Sequence Testing Procedure

Test	Variable	Comparison
1	Proportion of subjects with mean hemoglobin level during the evaluation period defined as Week 28 until Week 52 \geq 10.0 g/dL (U.S.) or Proportion of Hb responders in the average of weeks 28 to 36 within the target range of 10.0 to 12.0 g/dL without having received rescue therapy. (Ex-U.S.).	Non-inferiority of roxadustat versus EPO with margin of -0.15
2	LDL cholesterol change from BL to the average of weeks 12 to 28.	Superiority of roxadustat versus EPO
3	Hemoglobin change from baseline to the average level during Weeks 18 to 24 for subjects with baseline hsCRP > ULN	Non-inferiority of roxadustat versus EPO
4	Average monthly IV iron (mg) use per subject during weeks 28 to 52.	Superiority of roxadustat versus EPO
5	Time to first RBC Transfusion during the treatment.	Non-inferiority of roxadustat versus Epo with margin of 1.8
6	MAP change from BL to the average MAP of weeks 20 to 28.	Superiority of roxadustat versus EPO
7	Time to first exacerbation of hypertension: An increase from baseline of \geq 20 mmHg systolic blood pressure (SBP) and SBP \geq 170 mmHg or an increase from baseline of \geq 15 mmHg diastolic blood pressure (DBP) and DBP \geq 100 mmHg during Weeks 28 to 52.	Superiority and Non-inferiority of roxadustat versus EPO with margin of 1.8

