11.2.2.1 Proportion of Hemoglobin Responders

- US: Proportion of subjects with mean hemoglobin level during the evaluation period defined as Week 28 until Week 52 ≥ 10.0 g/dL, and patients with mean hemoglobin level between Hb 10-12 g/dL.
- Ex-US: Proportion of subjects with mean Hb between range of 10.0 to 12.0 g/dL without having received rescue therapy within 6 weeks prior to and during this 8-week evaluation period.

The hypothesis to be tested for the efficacy analysis is:

H0: Hemoglobin response rate for subjects in the roxadustat group - hemoglobin responder rate for subjects in the Epoetin group $\leq -15\%$

Versus

H1: Hemoglobin response rate for subjects in the roxadustat group - hemoglobin responder rate for subjects in the Epoetin group $> -15\%$.

A 2-sided 95% confidence interval for the difference of 2 responder rates (roxadustat – ESA) based on the Miettinen & Nurminen approach adjusting for treatment group and stratification factors will be calculated and non-inferiority will be declared if the lower bound of the 95% CI is greater than -15%.

Subjects who dropped out from the study before week 28 will be treated as non-responder.

11.2.2.2 Change from Baseline in LDL Cholesterol Averaged over Weeks 12 to 28

The change from baseline in LDL cholesterol will be analyzed and compared between the 2 treatment groups using MMRM model with baseline LDL cholesterol as a covariate and treatment group, visit, the interaction of treatment and visit, and the above mentioned stratification factors as fixed effects. The same strategy as that used in MMRM for Hb will be used to choose variance covariance structure. Data up to visit of Week 52 will be included in the model. The estimates for difference of LDL Cholesterol averaged over Weeks 12 to 28 between the two treatments groups will be generated from an estimate statement from Visit Week 12 to 28. Superiority will be declared if the upper bound of the 2-sided 95% confidence interval of the difference between roxadustat and active control does not exceed 0.

Baseline, LDL, is defined as the last available value obtained prior to the first dose of study drug.

11.2.2.3 Hemoglobin change from baseline to the average level during the Week 18 to 24 for Subjects with CRP > ULN

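### The LDL superiority test is valid for the total treatment difference, but no planned analysis separates roxadustat's own effect from statin changes in one arm, and one of two baseline LDL values goes unused

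*Protocol*

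**What the plan says.** Protocol 4.6.1.2 reports, from clinical pharmacology studies, a two- to threefold rise in statin exposure with roxadustat. It then says "The dose of statins should not exceed the recommended daily dose in the table below for subjects randomized to roxadustat", and the table that follows lists recommended daily maxima. Epoetin subjects have no matching text. The same section also says "Goals of lipid lowering treatment should be maintained as clinically indicated".

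SAP Table 6 lists "LDL cholesterol change from BL to the average of weeks 12 to 28" as Test 2, a superiority test. SAP 11.2.2.2 analyses it by MMRM with baseline LDL, treatment, visit, treatment by visit and the stratification factors. Those factors (SAP 11.1.1.1) do not include statin use, nor do the subgroups named in SAP 11.1.3 and 13. The only planned use of lipid-drug data is optional (SAP 10): "Detailed analyses may be performed on prior and concomitant medications of special interests such as oral iron, blood pressure medications and lipids medications".

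Lipid panels are scheduled at Screening 1 and on Day 1 before dosing (Protocol 7.1.1.1, 7.1.2.1). SAP 11.2.2.2 uses one of them: "Baseline, LDL, is defined as the last available value obtained prior to the first dose of study drug". For blood pressure and iron indices, SAP 5.4 averages the values from the 6 weeks before first dose.

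**The concern.** The effect on serum lipids is one of two secondary objectives, and Protocol 2.3 lists a better lipid profile among roxadustat's potential advantages over ESAs. A successful Test 2 is therefore likely to be read as a property of the drug.

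Two other things can move LDL after randomization, and both arise in roxadustat statin users only. Raised statin exposure would tend to lower LDL; a statin dose reduced to the recommended maximum would tend to raise it. The trial is open-label, so prescribers know which guidance applies. The LDL contrast adds these effects to any direct one, and nothing in the plan lets a reader see how much each contributes.

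The sponsor treats the parallel problem for blood pressure differently. Protocol 4.6.1 asks that changes in antihypertensive drugs be kept to a minimum to avoid confounding, and SAP 12.3 plans a subgroup with no such change. Statins have neither.

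The baseline point is separate and smaller: a second pre-dose LDL value is collected and then left out of the model.

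**Working it through.** **The plan's own figure.** The only power statement is for the hemoglobin endpoint. With 300 per arm, SD 1.25 and a distance to the margin of 0.75 - 0.30 = 0.45 g/dL, SE = 1.25 × √(2/300) = 0.102, and power = Φ(0.45/0.102 - 1.96) = 99.3%. The stated figure of at least 99% reproduces. It says nothing about LDL: the documents give no LDL SD, correlation or share of statin users. All LDL inputs below are assumptions, except the effect of about 20 mg/dL (Protocol 2.4.2.2, the Phase 2 study in China).

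**Statin contribution.** Contribution to the LDL contrast = share of statin users × net LDL change per user caused by statin changes in the roxadustat arm.

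- Share 30%, ±10 mg/dL per user: ±3.0 mg/dL.
- Share 50%, ±10: ±5.0 mg/dL.
- Share 70%, ±10: ±7.0 mg/dL.

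The net change can also be zero. If 20% of users have a dose reduction and gain 20 mg/dL while 80% lose 5 mg/dL through higher exposure, the net is 0.2 × 20 - 0.8 × 5 = 0.

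**What a statin term would do.** 1,000 simulated trials per row: N = 600, SD 30, equal correlation 0.7, half of subjects on statins with LDL 15 mg/dL lower, direct effect -20 mg/dL, one baseline value.

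| Net change per user | No statin term | Baseline statin main effect added | Baseline non-users only |
|---|---|---|---|
| -10 | -25.02 | -25.03 | -20.06 |
| 0 | -20.02 | -20.02 | -20.02 |
| +10 | -15.07 | -15.08 | -20.09 |

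The main effect leaves the estimate where it was, and the SE in the middle row moves only from 1.37 to 1.36. Baseline use is balanced by randomization in expectation; the mixing comes from what happens afterwards in one arm. Baseline non-users recover the direct effect, at an SE of 1.93. With equal halves, the treatment-by-statin interaction has an SE of about 1.93 × √2 = 2.7.

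**Second baseline value.** The window contains three lipid visits (Weeks 12, 20, 28; Protocol 7.1.2.3, 7.1.2.4). With unit variance and equal correlation ρ, the residual variance of their mean is (1 + 2ρ)/3 - ρ² given one baseline value, and (1 + 2ρ)/3 - 2ρ²/(1 + ρ) given the mean of two.

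| ρ | One | Two | Reduction |
|---|---|---|---|
| 0.5 | 0.417 | 0.333 | 20% |
| 0.6 | 0.373 | 0.283 | 24% |
| 0.7 | 0.310 | 0.224 | 28% |
| 0.8 | 0.227 | 0.156 | 31% |

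Equal correlation is favourable to averaging. With correlation a·exp(-gap/τ) and Screening 1 placed 4 weeks before Day 1, the reduction is 17% (a = 0.8, τ = 200 weeks), 12% (0.7, 100) or 5% (0.8, 60).

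**Power.** With N = 600 and an assumed SD of 30 to 40 mg/dL, power for 20 mg/dL is about 100% with either baseline. Only small effects are touched: at 5 mg/dL, SD 40 and ρ = 0.5, the SE falls from 2.11 to 1.89 and power rises from 66% to 76%.

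**The case against.** The strongest reply is that Test 2 answers the question asked. The objective is the effect on lipids compared with epoetin alfa; an interaction that roxadustat causes, and the prescribing guidance that comes with it, are part of that difference. Randomization protects the comparison. The protocol wording is guidance (should not exceed, recommended maximum), it asks that lipid goals be maintained, and a lower dose with higher exposure may leave a patient about where they started: half the dose at twice the exposure is the same exposure. On baseline, the last pre-dose value is the SAP's general default in 5.4.

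Most of this stands. A reader might infer that omitting baseline statin use biases Test 2, or that a statin covariate would cure the mixing; the simulation shows neither is so. A reader might also infer that statin doses have to be cut in the roxadustat arm, or that the LDL result will be distorted in a known direction. The text of 4.6.1.2 supports neither, and the 2- to 3-fold figure was not measured in this trial.

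What the reply does not cover is interpretation. The SAP does not say that Test 2 is a total difference, and it plans nothing to show how much of it arises in statin users. For the baseline, no reason is given for not using the second value that is already scheduled.

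**Conclusion.** The point holds as a cheap improvement to interpretation and precision, not as an error in the test. Test 2 and its place ahead of Tests 3 to 7 remain valid for the total LDL difference under assigned treatment. The gap is that an LDL difference cannot be attributed to roxadustat itself, because statin exposure and dose may change after randomization in that arm only. The contribution is -7 to +7 mg/dL under the assumed shares and shifts, that is, up to about a third of the 20 mg/dL Phase 2 effect (7/20 = 35%). Its sign is unknown, and zero is possible.

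The single LDL baseline gives up about 5-31% of residual variance, depending on the assumed correlations. It would be wrong to read this as a power problem: near 20 mg/dL the test has ample power either way.

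**What to change.** **Baseline (SAP 11.2.2.2).** Define baseline LDL as the mean of the central-laboratory values within 6 weeks before first dose, as SAP 5.4 does for blood pressure and iron indices. Screening can last 8 weeks for Mircera subjects, so add a fallback: if only one value lies in the window, use it; if none does, use the last pre-dose value. Apply the same rule to total and non-HDL cholesterol (SAP 11.3.4), and align the Day 1 baseline window in SAP Table 13.

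**Attribution (SAP 11.2.2.2).** State that Test 2 estimates the total difference under assigned treatment. Prespecify, as supportive and outside the testing sequence, the same LDL contrast by baseline statin use (yes/no) with the treatment-by-statin interaction. Baseline non-users give the reading free of the interaction, unless they start a statin. Add a by-arm summary of statin starts, stops and dose changes through Week 28. Keep that summary descriptive, because groups formed by changes after randomization are not randomized comparisons.

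A baseline-statin main effect may be added for a slight gain in precision, but it should not be presented as removing the mixing.

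**Cost.** SAP wording and a few extra outputs. Lipid panels and concomitant medications are already scheduled; the documents do not say whether the medication form records dose, so confirm that first. The subgroup reading is less precise (SE 1.93 against 1.37 in the example). The clinical guidance on statins needs no change for this.
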